#### UVEDERM VOLUMA° XC injectable gel

| Table 1-4 Tre  | eatment Grou                                   | p Procedures                             | s: Maintenan                                 | ce Treatment                                 | and Follow-u                                 | ıp Period  |
|--|--|--|--|--|--|--|
| Procedure  | Main   | tenance Trea                             | Follow-up                        | )  |  |  |
|  | Maintenance
Treatment a
Visit | 3 Days After
Maintenance
Treatment | 14 Days
After
Maintenance
Treatment | Month 1
After
Maintenance
Treatment | Month 3
After
Maintenance
Treatment | Month 6 After
Maintenance
Treatment/Exit
Visit c |
| Visit Window (Days)  |  | ± 2                                      | + 4  | + 10   | ± 7  | ± 15   |
| Urine pregnancy test d  | Xe   |  |  |  |  | X  |
| 3D facial digital imaging  | Xf   |  | Х  | Х  | Х  | Х  |
| Vision Assessments: (TI or   |  |  |  |  |  |  |
| designee)  |  |  |  |  |  |  |
| 

Snellen visual acuity

Confrontational visual fields

  | X g                                 |  | х  | х  |  |  |
| 
 
Ocular motility
 
  |  |  |  |  |  |  |
| Study intervention,
intervention characteristics
(TI)  | х  |  |  |  |  |  |
| Procedural pain (Participant)  | Х  |  |  |  |  |  |
| Safety telephone call (TI)   |  | Х  |  |  |  |  |
| Safety e-diaryh (Participant)  |  | Continuous                               |  |  |  |  |
| FACE-Q (Participant)   |  |  |  |  |  |  |
| 
 
Satisfaction with Facial
Appearance
 
Satisfaction with
Temples
 
   |  |  |  | х  | х  | х  |
| Treatment Satisfaction
Questions (Participant):   |  |  |  |  |  |  |
| 
 
Satisfaction with
treatment
 
Natural look and feel of
the results
 
How treatment met
expectation
 
 |  |  |  | Х  | X  | Х  |
| 

Likelihood of continuing
the treatment

Willingness to
recommend treatment

                                      |  |  |  |  |  |  |
| Self-perception of age
(Participant)  |  |  |  | Х  | Х  | Х  |
| Jaw Functional Limitation
Scale (Participant)   |  |  | х  | х  |  |  |
| GAIS (Participant)   |  |  |  | Х  | Х  | Х  |
| ATHS (EI)  |  |  |  | Х  | Х  | Х  |
| GAIS (EI)  |  |  |  | Х  | Х  | Х  |
| Adverse events i  |  |  | Continuou                                    | is monitoring                                |  |  |
| Concomitant medications and concurrent procedures  |  |  | Continuou                                    | s monitoring                                 |  |  |

- a A maintenance treatment is offered to participants who complete the Month 13 visit. The procedures must occur no later than 14 days after the Month 13 visit.
- b Follow-up visit schedule is based on the date of the last study intervention (ie, maintenance treatment).
- c If a participant withdraws for any reason prior to the final study visit, attempts will be made to perform assessments at an exit visit.
- d For female participants of childbearing potential. A female is not considered of childbearing potential if she has been postmenopausal for at least 1 year or does not have a uterus at the time of study entry.
- e Administered and confirmed negative prior to study intervention. If maintenance treatment is done on the same day of the Month 13 visit, this assessment does not need to be repeated.
- f Prior to maintenance treatment. If maintenance treatment is done on the same day of the Month 13 visit, this assessment does not need to be repeated.
- g Vision assessments will be performed by TI (or designee) before study intervention and at least 30 minutes after completing the injection procedures.
- h The safety e-diaries are to be completed following each study intervention starting on the day of treatment.
- i Will include a general, nondirected question about vision symptoms.

a month = 30 days

#### Protocol 1878-702-008 Amendment 2

#### Table 1-5 Control Group Procedures: Control Period

| Procedure  | Randomization a | Follow-up b |                                     |  |
|--|-----------------------------------|------------------------|-------------------------------------|--|
|  |                                   | Month 1                | Month 3/
Study Exit e |  |
| Visit Window (Days)                                      |                                   | +10                    | ± 7                                 |  |
| Urine pregnancy test d                        | Х                                 |                        |                                     |  |
| ATHS (EI) e                                   | X f                    | Х                      | Х                                   |  |
| Inclusion/exclusion criteria (TI)                        | Xf                                |                        |                                     |  |
| 3D facial digital imaging                                | Xf                                | Х                      | Х                                   |  |
| FACE-Q Satisfaction with Facial Appearance (Participant) | Xf                                | Х                      | Х                                   |  |
| FACE-Q Satisfaction with Temples (Participant)           | Xf                                | Х                      | Х                                   |  |
| Self-perception of age (Participant)                     | Xf                                |                        |                                     |  |
| Jaw Functional Limitation Scale (Participant)            | Xf                                |                        |                                     |  |
| Randomization  | Х                                 |                        |                                     |  |
| GAIS (Participant)                                       |                                   | Х                      | Х                                   |  |
| GAIS (EI)  |                                   | Х                      | Х                                   |  |
| Weight   |                                   |                        | Х                                   |  |
| Adverse events (TI)                                      | Continuous monitoring             |                        |                                     |  |
| Concomitant medications and concurrent procedures (TI)   | Continuous monitoring             |                        |                                     |  |

a month = 30 days

a Randomization must occur within 30 days of screening; screening visit and randomization visit can occur on the same day if participants do not require washout. If screening and randomization visits occur on the same day, inclusion/exclusion criteria, ATHS, and urine pregnancy test need not be repeated.

b During the control period, all follow-up visits are scheduled from the date of randomization.

c At the Month 3 visit, the TI will discuss the option for the control group participant to receive study intervention. Participants who accept optional treatment, after completing the procedures under Month 3, will undergo the additional procedures specified in Table 1-6. Participants who do not accept optional treatment will exit the study after the Month 3 procedures are completed.

d For female participants of childbearing potential. A female is not considered of childbearing potential if she has been postmenopausal for at least 1 year or does not have a uterus at the time of study entry.

e TI will use EI ATHS scores to confirm participant's eligibility in the study.

f Done prior to randomization.

Protocol 1878-702-008 Amendment 2

Table 1-6

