| Adverse events e (TI)   |                                  | Con     | tinuous mor | nitoring |   |
| Concomitant medications and concurrent procedures
(TI)  | Continuous monitoring            |         |             |          |   |

a month = 30 days

a The follow-up visit schedule is based on the date of the last study intervention (ie, if no touch-up treatment is performed, the Month 1 visit occurs 30 days after initial treatment; if touch-up treatment is performed, the Month 1 visit occurs 30 days after touch-up treatment).

b At the Month 13 visit, participants will be offered a maintenance treatment after completion of the Month 13 visit. Participants who accept maintenance treatment will undergo the additional procedures specified in Table 1-4. Participants who do not accept maintenance treatment will exit the study after the Month 13 procedures are completed.

c If a participant withdraws for any reason prior to the final study visit, attempts will be made to perform assessments at an exit visit.

d For female participants of childbearing potential. A female is not considered of childbearing potential if she has been postmenopausal for at least 1 year or does not have a uterus at the time of study entry.

e Will include a general, nondirected question about vision symptoms.

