#### 4. Study Design

#### 4.1. **Overall Design**

The design elements of this protocol have been reviewed with patients to obtain their perspectives in the following areas: schedule of events, length of study and visits, randomization ratio and duration of control period, and ICF language on possible adverse events.

This is a prospective, multicenter, evaluator-blinded, randomized, parallel-group, controlled study to evaluate the safety and effectiveness of VOLUMA XC injectable gel to correct temple hollowing.

The study will involve up to 15 investigational sites. The study population is represented by adults who are seeking correction of the temple hollowing and who meet the study criteria according to the study design.

Participants will be randomized on study intervention day in a 2:1 ratio of treatment group to control group.

Participants will stay in the study for up to 21 months depending on their randomization group. For the treatment group, each participant will be in the study for up to 21 months: up to 1 month for screening, up to 30 days of treatment, up to 13 months of follow-up after initial/touch-up treatment, and up to 6 months of follow-up after maintenance treatment. For the control group, each participant will be in the study for up to 4 months (up to 1 month for screening and 3 months for follow-up) and then may exit or opt to receive study intervention. Control participants who opt to receive study intervention will be in the study for an additional 14 months (up to 30 days for treatment and 13 months of follow-up), for a total of up to 18 months.

[figure not shown]
|                                 | Treatment Group | Control Group        |
|---------------------------------|------------------------|----------------------|
| Screening                       | Up to 1 month          | Up to 1 month        |
| Control period                  | Not Applicable         | 3 Months             |
| Treatment period                | 1-30 Days              | 1-30 Days (optional) |
| Treatment follow-up period      | 13 Months              | 13 Months            |
| Maintenance treatment           | 1 Day (optional)       | Not Applicable       |
| Maintenance treatment follow-up | 6 Months               | Not Applicable       |

The study will compare the treatment to no treatment, with the primary timepoint set at Month 3.

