#### CONFIDENTIAL JUVÉDERM VOLUMA® XC injectable gel

#### 6. **Study Intervention**

Study intervention is defined as any investigational intervention(s), marketed product(s), placebo, or medical device(s) intended to be administered to a study participant according to the study protocol.

Participants may undergo a touch-up treatment 30 days after the initial treatment if agreed upon by both the participant and TI. See Section 6.6.1 for details.

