5.0 Participant Disposition

5.1 Study Period

The study periods are defined below in Table 2 for VOLUMA XC group and control group. For VOLUMA XC group, the Treatment Period (TP) is the Control Period (CP) plus the Post-Control Period (PCP). For participants in the control group, the TP starts on the date of optional treatment and ends on the same day as the study exit.

Table 2. Definition of the Control, Treatment and Maintenance Treatment Periods by Analysis Group (as-randomized for effectiveness or as-treated for safety)

Analysis Group	Period	Analysis Group Label	Start Date	End Date
VOLUMA	CP	VOLUMA XC	Initial treatment date	
The end date is the date of the Month 3 assessment:
 
 • If multiple assessments fall into Month 3 window, the date of the assessment included in the Month 3 analysis will be used as end date. • For participants who exit before Month 3, the end date is study exit date. • For participants with a missing assessment at Month 3, the end date is the target day for Month 3 (90 days from preceding treatment).
	TP	VOLUMA XC	Initial treatment date	Date of maintenance treatment or the study exit date, whichever is earlier
	MP	VOLUMA XC	Maintenance treatment date	Study exit date
Control	CP	Control	Randomization date	
For participants who do not receive optional treatment:
 
 • If multiple assessments fall into Month 3 window, the date of the assessment included in the Month 3 analysis will be used as end date. • For participants who exit before Month 3, the end date is study exit date. • For participants with missing assessment at Month 3, the target day for Month 3 (Day 91) will be the end date. 
For participants who receive optional treatment, the end date is the date of optional treatment.

	TP	VOLUMA XC Post-Control	Optional initial treatment date	Study exit date

The start and end of treatment periods listed above for the mis-treated participants (ie., randomized to treatment and did not receive VOLUMA XC or randomized to control and was treated with VOLUMA XC prior to the primary timepoint) will be determined based on the treatment received.

For CP, effectiveness analyses and baseline characteristics will be performed on the mITT population using the "as-randomized" assignment.

For TP, effectiveness and safety summaries will be performed on the VT population by treatment group.

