9.2.2 Adverse Event Overview

TEAEs will be summarized by treatment group for CP using the safety population. TEAEs will also be summarized by treatment group for TP and MP using the VT and VMT populations, respectively as described in Table 9. The summaries will be presented using number and percentage of participants with TEAEs as well as the number of events. Additional summaries may be provided when applicable.

An overall summary of TEAEs will be presented as described in Table 9.

Treatment-related AEs will be summarized by duration, severity, time to onset on/after the most recent treatment, and outcome.

The duration of an AE is defined as the end date of AE minus the start date of AE plus 1.

For participants who received maintenance treatment, their AEs reported during the first 6 months from the initial treatment will be summarized and presented in parallel with AEs reported during the maintenance treatment period. The summary for the initial treatment will be presented for participants who received initial treatment only and participants who received both initial and touch-up treatments.

If more than 1 AE is coded to the same preferred term for a participant, the participant will be counted only once for that preferred term using the most severe and most related occurrence for the severity and relationship to study intervention summaries, respectively.

If the severity of a TEAE is missing, the maximum severity will be assigned to the event for the summary on severity. The value will be displayed as missing in the data listing.

If the relationship to the study intervention is missing for a TEAE, the event will be considered related to the study intervention for the summary. The value will be displayed as missing in the data listing.

Listings of all AEs, TESAEs, TEAEs leading to discontinuation, and death will be presented.

Table 9. TEAE Summaries

Endpoint	Description	Timing	Methodology
Overall summary	Overall summary only for the following categories: 
 • TEAEs • Treatment-related TEAEs • Treatment-related TEAEs at injection site • Treatment-related TEAEs not at injection site • TESAEs • Treatment-related TESAEs • Treatment-related TESAEs at injection site • Treatment-related TESAEs not at injection site • Discontinued due to TEAEs • AESIs • Treatment-related AESIs • Deaths • TEAEs related to COVID-19 infection 	CP, TP, MP	Frequency counts and percentages

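### Control-period adverse-event percentages may differ between groups through observation time alone: a touch-up lengthens the VOLUMA period, optional treatment lengthens the control period, and SAP 9.2.2 allows for neither

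*Protocol*

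**What the plan says.** **Visit anchors.** For controls, Protocol Table 1-5 says "During the control period, all follow-up visits are scheduled from the date of randomization", and "a month = 30 days". For the treatment group, Protocol Table 1-3 counts follow-up from the last injection: "if touch-up treatment is performed, the Month 1 visit occurs 30 days after touch-up treatment". SAP 8.3.3 defines Month 3 in the same asymmetric way.

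**Touch-up.** It is optional: "Participants may undergo a touch-up treatment 30 days after the initial treatment if agreed upon by both the participant and TI" (Protocol Section 6). Table 1-2 gives that visit a window of +10 days. Section 4.1 describes "up to 30 days of treatment".

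**Period dates.** In SAP Table 2 the VOLUMA control period starts at "Initial treatment date" and ends at the Month 3 assessment. The control group's period starts at randomization and ends at Month 3, with one exception: "For participants who receive optional treatment, the end date is the date of optional treatment". Protocol Table 1-6 allows that treatment up to 14 days after the Month 3 visit.

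**Adverse-event summaries.** SAP 9.2.2 summarizes control-period TEAEs by group in the safety population: "The summaries will be presented using number and percentage of participants with TEAEs as well as the number of events". Table 9 gives frequency counts and percentages as the method throughout. SAP 8.1 says that the Table 2 periods are meant to allow for treatment timing and make data-collection time frames comparable.

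**The concern.** A percentage of participants with any event rises with the time they are watched. Table 2 starts the VOLUMA clock at the first injection but ends it at a visit that a touch-up pushes back, so the time before the touch-up is extra observation. Controls have no touch-up. Their period can lengthen in another way, through the wait for optional treatment. Neither extension is matched in the other group, and neither is allowed for in the summaries.

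The control period is the only part of the trial with a randomized, untreated comparator for safety. If observation time differs between the groups, part of any difference in all-cause TEAEs reflects follow-up and not the device, and raw percentages cannot show how much or in which direction. Event counts have the same problem.

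**Working it through.** **1. The plan's own figure.** Month 3 = 3 x 30 = 90 elapsed days. With Day 1 as the start, that is Day 91, which matches the control target day in SAP Table 2.

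**2. Length of the control period.** The Month 3 window is ±7 days in both arms (Protocol Tables 1-3 and 1-5), so 83-97 days from the anchor.

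- VOLUMA, no touch-up: 83-97 days.
- VOLUMA, touch-up at 30-40 days (Table 1-2): 30 + 83 = 113 to 40 + 97 = 137 days.
- VOLUMA, touch-up no later than 30 days (as Section 4.1 words it): 30 + 83 = 113 to 30 + 97 = 127 days.
- Control, no optional treatment: 83-97 days.
- Control, optional treatment: up to 97 + 14 = 111 days.

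The touched-up range does not overlap either control range.

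**3. Effect on one participant's risk.** Assume a constant background hazard, equal in both groups, with risk p in 90 days. The risk over t days is F(t) = 1 - (1 - p)^(t/90). For p = 20%:

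- F(90) = 20.0%
- F(97) = 21.4%
- F(104) = 22.7%
- F(120) = 25.7%
- At the ends of the touched-up range, F(113) = 24.4% and F(137) = 28.8%.

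**4. Effect on the group percentages.** Let f be the touch-up share (120 days if touched up, otherwise 90). Let g be the share of controls taking optional treatment at 90 + d days.

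Difference = f x [F(120) - F(90)] - g x [F(90 + d) - F(90)]

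The documents do not give p, f, g or d. All values below are assumptions. At p = 20% the first bracket is 5.73 points. With f = 30% it contributes 1.72, and with f = 70% it contributes 4.01. The control terms are:

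- g = 0: 0.
- g = 80%, d = 7: 0.8 x 1.38 = 1.10.
- g = 100%, d = 14: 2.73.

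Difference in percentage points, VOLUMA minus control, for f = 30% to 70%:

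| Controls | p = 10% | p = 20% | p = 30% |
|---|---|---|---|
| All stop at 90 days | +0.9 to +2.2 | +1.7 to +4.0 | +2.4 to +5.5 |
| 80% treated 7 days after Month 3 | +0.3 to +1.6 | +0.6 to +2.9 | +0.8 to +4.0 |
| All treated 14 days after Month 3 | -0.5 to +0.7 | -1.0 to +1.3 | -1.4 to +1.7 |

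At p = 20% the sign changes at a touch-up share of 1.10 / 5.73 = 19% in the second row and 2.73 / 5.73 = 48% in the third.

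**The case against.** A reader might infer that the groups are bound to differ, with VOLUMA always looking worse. The documents do not support that. The 113-137 days belong only to touched-up participants; the others have the same 83-97 days as controls without optional treatment. Optional treatment lengthens control observation and can cancel or reverse the imbalance. With neither uptake given, only the possibility of a difference is established. The 137-day end also stacks the extremes of two windows.

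A reader might also infer a flawed test. The legible text plans no formal test of adverse events, so the comparison is descriptive. The point concerns all-cause events: controls are not injected, so injection site responses and procedural pain have no control counterpart. Treatment-related events are also summarized by duration, severity, outcome and time to onset from the latest treatment, and SAP 9.2.2 leaves room for additional summaries. These are useful, but none of them prespecifies an allowance for time at risk.

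Observation time is not the only asymmetry. Participants and treating investigators are unblinded. VOLUMA participants have safety calls, Day 14 visits and e-diaries, while controls have only the Month 1 and Month 3 visits in this period. That gap in ascertainment would remain after any correction for time.

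Counting follow-up from the last injection is a deliberate rule, and it is not the defect. What stands is narrower: the periods differ in length by design, and the safety summaries do not allow for it. SAP 9.2.2 already matches windows elsewhere, restricting initial-treatment events to the first 6 months when setting them beside the maintenance period.

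**Conclusion.** The point holds in conditional form, as a minor improvement. The day ranges follow directly from the stated anchors and windows, and SAP 9.2.2 and Table 9 are legible and contain no time-at-risk denominator or common cut-off. The Table 2 periods therefore do not secure, for the control period, the comparability that SAP 8.1 sets as their aim.

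The distortion could be a few points either way: across the assumed scenarios, from -1.4 to +5.5. These figures rest on a constant and equal background hazard of 10-30% in 90 days, a touch-up share of 30-70% and three patterns of optional treatment. They illustrate scale and do not predict this trial's result.

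**What to change.** Keep the planned percentages. In SAP 9.2.2 and Table 9, add one control-period table counting TEAEs in both groups from Day 1 to the same day, for example Day 91, the SAP's own control target for Month 3. Exposure-adjusted incidence from the Table 2 dates can be an optional supplement. Under an equal constant hazard and complete follow-up to the cut-off, the common window brings the expected difference to zero.

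The cost is one extra table from dates already collected. The SAP should state the limits:

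- The common cut-off leaves touched-up participants with only 90 - 40 = 50 to 90 - 30 = 60 days after the touch-up, so the planned full-period summary is still needed.
- Person-time rates can dilute events that cluster soon after injection. The same early events spread over 120 instead of 90 days give a rate 25% lower (90/120 = 0.75). The common-window table should therefore lead.
- Neither table removes the difference in adverse-event ascertainment between the unblinded arms.

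Separately, the +10-day touch-up window in Protocol Table 1-2 and the length of the treatment period in Section 4.1 must be reconciled, since they give different upper limits (137 or 127 days).
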